8.7 Visit Windows

Visit windows are based on Study Day. Observations will be assigned to an analysis window according to the tables below. Observations that cannot be assigned to an analysis window based on the tables below will be excluded from summaries and analyses (but will still be listed). For subjects not dosed, planned date of first dose will be used in Study Day calculations, if necessary.

For otoscopy and tympanogram parameters:

Nominal Visit	Target Study Day	Min Study Day Per Protocol	Max Study Day Per Protocol	Min Study Day for Analyses	Max Study Day for Analyses
Visit 1 (Day 1 Pre-Dose)	1 (pre-dose)	1	1 (pre-dose)	N/A	1 (pre-dose)
30 Minutes Post-Dose	1 (post-dose)	1 (post-dose)	1 (post-dose)	1 (post-dose)	1 (post-dose)
Visit 2 (Day 4)	4	4	6	4	6
Visit 3 (Day 12)	12	12	14	12	14
Visit 4 (Day 28)	28	26	30	26	30

N/A, not applicable

Confidential Page 15 of 35

Nominal Visit	Target Study Day	Min Study Day Per Protocol	Max Study Day Per Protocol	Min Study Day for Analyses	Max Study Day for Analyses
Visit 1 (Day 1)	1 (pre-dose)	1	1 (pre-dose)	N/A	1 (pre-dose)
Visit 2 (Day 4)	4	4	6	4	6
Visit 3 (Day 12)	12	12	14	12	14
Visit 4 (Day 28)	28	26	30	26	30

N/A, not applicable

For AOM-SOS score collected by diary:

Nominal Visit	Target Study Day	Min Study Day Per Protocol	Max Study Day Per Protocol	Min Study Day for Analyses	Max Study Day for Analyses
Visit 1 (Day 1)	1 (pre-dose)	1	1 (pre-dose)	N/A	1 (pre-dose)
Diary Day x, x=2-10	X	X	X	X	X

N/A, not applicable

If multiple valid, non-missing observations exist within a given window, the observation to be used will be:

- 1. the observation closest to the target study day of the nominal visit in question, or
- 2. the latest observation if the multiple observations are equidistant from the target study day of the nominal visit, or
- 3. the average (arithmetic or geometric, as appropriate) of the observations if the multiple observations have the same actual time point.

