12.4 AOM-SOS Scale

The AOM-SOS scale is scored by the parent/caregiver once daily at home and recorded in a diary over the 10-day duration of the antibiotic and study treatment period and also at in-clinic visits on Day 1, 4, 12 and 28. The scale consists of 5 questions rated on a 6-point scale, with lower scores associated with better symptom status: 0 = no, 1 = almost none, 2 = a little, 3 = some, 4 = a lot, 5 = an extreme amount. A total score for each day will be calculated in the AOM-SOS analysis data set (ie, not in the eCRF) as the sum of the 5 individual scores. Missing observations for individual questions will not be possible, which is a built-in feature of the data collection instrument; either all 5 questions will have responses or none of the 5 questions will have responses.

At the screening visit the parent/caregiver will be asked to score the AOM-SOS scale as part of the screening criteria for the study; a score of at least 5 is an inclusion criterion. This is the only baseline assessment of the AOM-SOS scale.

Confidential Page 24 of 35

Listings for AOM-SOS scale will show observed values at each time point collected for both diary and in-clinic, the 10-day mean from diary, and absolute and percent changes from baseline in the in-clinic AOM-SOS scores for Days 4, 12, and 28.

Endpoints

Secondary endpoints based on the AOM-SOS scale will be:

- 10-day mean AOM-SOS total score based on diary data, calculated for each subject as the mean total score over the 10-day treatment period. If the Day 4 assessment is missing from the diary, the Day 4 in-clinic assessment may be used but only if done on Study Day 4. If more than 10 days of AOM-SOS scores are available, only the first 10 days will be used to calculate the mean. If less than 10 days of AOM-SOS scores are available, 10-day mean score will not be calculated.
- Complete or near complete resolution of symptoms (AOM cure), defined as in-clinic AOM-SOS score < 2, assessed at the Day 4, 12, and 28 visits.
- AOM-SOS response, defined as at least a 50% reduction from baseline in the in-clinic AOM-SOS score, assessed at the Day 4, 12, and 28 visits.

Since a Day 4 assessment should be available from both the diary and the in-clinic visit, the in-clinic assessment will be used for the resolution and response endpoints. If the in-clinic assessment is not available, the Day 4 diary assessment will be used.

In a sensitivity analysis, AOM cure will be defined as AOM-SOS score = 0.

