Summaries and Analyses (see Section 13)

The 10-day mean AOM-SOS total score will be analyzed using a general linear model (GLM) with baseline AOM-SOS total score included as a covariate. A summary table will include means and SDs for each treatment group and a p-value for the difference.

AOM cure and AOM-SOS response will be summarized and analyzed separately by visit using logistic regression with baseline AOM-SOS total score included as a covariate. Summary tables will include frequencies and percentages of AOM cure and AOM-SOS response for each treatment group by visit and p-values for the differences.

12.5 **AOM Treatment Failure**

AOM treatment failure (clinical failure) will be defined as:

- moderate to severe bulging of the TM, or
- mild bulging of the TM with
 - o recent (less than 48 hours) onset of ear pain (otalgia), or
 - o intense erythema of the TM

AOM treatment failure (clinical failure) will be available in the eCRF and will not be programmatically derived. As a cross-check, a listing will be provided that shows degree of bulging TM, otalgia, and erythema in each ear and AOM treatment failure status at Day 12.

Confidential Page 25 of 35

Endpoints

AOM treatment failure (clinical failure) at the Day 12 visit will be a secondary endpoint.

Summaries and Analyses (see Section 13)

AOM treatment failure (clinical failure) will be analyzed using logistic regression. A summary table will include frequencies and percentages of treatment failure and a p-value for the treatment group difference.

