13.3 Missing Observations

For the primary efficacy analysis, multiple imputation will be used for missing observations with only treatment group included in the imputation model; ie, the observed within-treatment-group Bernoulli distribution of response will be the distribution from which random values are drawn to replace missing observations. The number of imputations will be the percentage of subjects with missing data, rounded up to an integer. Results from multiple imputations will be combined using the Rubin method.⁸ A complete-case sensitivity analysis will also be done, whereby for each endpoint only subjects with complete data are included. For secondary endpoints, only complete-case analyses will be done.

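### The 10-day diary AOM-SOS mean needs ten scores, but the SAP windows hold only nine post-dose days, so baseline must count and almost any missed entry drops the child

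*SAP*

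**What the plan says.** SAP 12.4 turns the diary endpoint into one number per child, the mean total score over the 10-day treatment period. Three rules govern it:

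- Too few scores: "If less than 10 days of AOM-SOS scores are available, 10-day mean score will not be calculated".
- Too many scores: "If more than 10 days of AOM-SOS scores are available, only the first 10 days will be used to calculate the mean".
- One substitute: if the Day 4 diary entry is missing, "the Day 4 in-clinic assessment may be used but only if done on Study Day 4".

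Of the screening score, the same section says: "This is the only baseline assessment of the AOM-SOS scale". The 10-day mean is then analysed with a "general linear model (GLM) with baseline AOM-SOS total score included as a covariate".

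The diary table in SAP 8.7 has a Day 1 row that ends at pre-dose, and one further row, "Diary Day x, x=2-10". Above the tables stands the general rule: "Observations that cannot be assigned to an analysis window based on the tables below will be excluded from summaries and analyses". SAP 13.3 adds: "For secondary endpoints, only complete-case analyses will be done".

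Protocol 4.1 has caregivers complete the diary on every treatment day, approximately ten days. Protocol 9.4.1 allows mean differences to be analysed with either general linear models or mixed models for repeated measures.

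**The concern.** Sections 8.7 and 12.4 do not fit together. Under the 8.7 windows ten scores can be reached only by counting the pre-dose score, yet 12.4 never says that it belongs in the mean. Section 12.4 also provides for more than ten scores, which the windows make impossible. If 12.4 overrides the windows, an entry on Day 11 could fill a gap; if 8.7 governs, it cannot. Two programmers working from the same SAP could build different analysis sets.

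The larger issue is the all-or-nothing rule. A child with eight of nine post-dose scores contributes nothing, and complete-case analysis offers no way back. The comparison is then confined to families with a full diary. They may differ from the rest, for example if caregivers stop recording once a child recovers or worsens. Section 16 declares complete-case analysis of secondary endpoints but does not mention the ten-of-ten requirement.

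**Working it through.** **Counting the windows (SAP 8.7).** Day 1 pre-dose gives 1 and Days 2 to 10 give 9, so 1 + 9 = 10. The required ten is met exactly when baseline is included; without it the maximum is nine. A miss on any of the eight days 2, 3 and 5 to 10 always removes the child. A miss on Day 4 does so unless the clinic score was taken on Study Day 4, while the visit window runs from Day 4 to Day 6.

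**How many children keep a value.** The documents give no completion rate, so the daily rate q is assumed. The base is 140 planned (SAP 5) less the 3 excluded from the mITT population (SAP 7), which is 137.

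- Independent days, no Day 4 backup: q^9. For q = 0.95, 0.95^9 = 0.630, and 0.630 × 137 = 86.
- Independent days, Day 4 always backed up: q^8. For q = 0.95, 0.95^8 = 0.663, and 0.663 × 137 = 91.
- Misses clustered within families, no backup: beta-binomial probability of nine out of nine, with assumed within-family correlation 0.1 to 0.3.

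| Daily completion | No backup | Day 4 backed up | Clustered |
|---|---|---|---|
| 98% | 83% (114) | 85% (117) | 88–92% |
| 95% | 63% (86) | 66% (91) | 72–81% |
| 90% | 39% (53) | 43% (59) | 51–65% |

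**Precision.** The standard error relative to keeping all 137 is 1/√(share kept). At 95% completion it is 1.26 with no backup, 1.23 with Day 4 backed up and 1.11–1.18 clustered. At 90% it is 1.61, 1.52 and 1.24–1.40. Dropout before Day 10 comes on top.

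**Counting baseline.** Let B be the baseline score and Y the mean of Days 2 to 10. The ten-score mean is 0.1B + 0.9Y. With B already a covariate, the 0.1B term is absorbed, so the treatment coefficient and its standard error are both multiplied by 0.9 and their ratio is unchanged. In one simulated data set the estimate goes from −1.399 to −1.399 × 0.9 = −1.259, and the SE from 0.459 to 0.459 × 0.9 = 0.413. In both cases t = −3.048 and p = 0.0028.

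**Comparing methods by simulation.** All inputs are assumed: 300 data sets of 137 children, normal scores falling over Days 2 to 10, true mean difference −1.0, 5% random missed days, no Day 4 backup, and a 20% chance of stopping after a recorded score below 2. Missingness is at random here, which favours the repeated-measures model. Monte Carlo error is about 0.03.

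| Method | Mean estimate | SD |
|---|---|---|
| No missing data | −0.995 | 0.355 |
| Complete diaries only (50% kept) | −0.88 | 0.485 |
| Mean of available days, at least 5 | −0.88 | 0.346 |
| Repeated-measures model | −0.99 | 0.360 |

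With random missed days only, complete diaries give −1.03 (SD 0.441) and the repeated-measures model −0.98 (SD 0.352).

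**The case against.** The strongest reply is that 12.4 is the endpoint-specific text and may be meant to override the general windows. An entry outside the windows could then fill a gap, and it would no longer follow that baseline must count. That reading is possible, but 8.7 excludes such entries in plain terms and has a table specifically for the diary. The conflict itself is enough to require a change. One could also argue that a Day 1 row plus Days 2 to 10 makes exactly ten, so counting Day 1 is implied. If so, the SAP should state it, because the same score is the covariate.

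Several limits stand:

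- The loss is wholly assumed. Protocol 1.3 and 6.4 plan diary checks and retraining, so completion may be high, and nothing in the documents shows selective stopping.
- With purely random misses, complete diaries lose precision but show no clear bias.
- The factor 0.9 is exact only for the baseline-adjusted difference. The difference in raw means also carries 0.1 times any baseline imbalance.
- The protocol sets no diary-completeness rule and leaves missing-data handling to the SAP, so the omission from Section 16 is a minor point.
- Requiring a minimum number of days would also end the all-or-nothing loss: at least 7 of 9 keeps 99.2% of children at 95% independent daily completion. But symptoms fall over time, so early stoppers would get inflated means.

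Normal scores are also a simplification for a 0 to 25 integer scale. In a further check with rounded scores floored at zero, the repeated-measures model stayed close to the full-data result (−1.06 against −1.03, SD 0.26 against 0.25). Complete diaries kept 46% of children, with SD 0.40.

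**Conclusion.** The concern holds and should be fixed. Under the windows as written, the ten-score rule works only if baseline counts, and it leaves no room for a missed entry except, conditionally, on Day 4. At an assumed 95% daily completion, between 63% and 81% of children would keep a value, depending on Day 4 backup and clustering; at 90%, between 39% and 65%. Counting baseline affects the size of the reported effect, not the test. The reach is limited: this is one secondary endpoint without multiplicity adjustment, meant to guide future studies, and the primary conclusions do not depend on it.

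**What to change.** Amend the SAP before database lock:

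1. Remove the ten-of-ten rule. Analyse Days 2 to 10 with a mixed model for repeated measures containing treatment, day, treatment-by-day, baseline score and the randomization stratifiers. Use an unstructured covariance, with a named fallback if the model does not converge. Report the average treatment difference over Days 2 to 10.
2. Use the pre-dose score only as a covariate, and keep the Study Day 4 clinic backup.
3. Delete the sentence on more than ten days in 12.4, or reconcile it with the 8.7 windows.
4. Keep the complete-diary mean over Days 2 to 10 as a sensitivity analysis, and report the number of diary days per child by arm.
5. List the change in Section 16.

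The cost is SAP wording and one model, with no new data. There are two downsides. The model assumes that data are missing at random. Nine time points also mean 9 × 10 / 2 = 45 covariance parameters, which is why the fallback must be named in advance.

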### Number of Participants:

Approximately 140 Participants with AOM in at least 1 ear will be randomly assigned to study treatment such that approximately 70 evaluable Participants per treatment group complete the study.

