All secondary efficacy endpoints will be evaluated in the safety population, without adjustment for multiplicity; therefore, p-values for these endpoints will be used only to aid in decision-making regarding whether any should be elevated in importance in future studies. These endpoints are:

- No MEE assessed at the Day 4 Visit and the Day 28 Visit by pneumatic otoscopy.
- No bulging of the TM assessed at the Day 12 Visit and the Day 28 Visit by pneumatic otoscopy.
- Normal tympanogram (Type A) assessed at the Day 4 Visit, the Day 12 Visit, and the Day 28 Visit by tympanometry.
- Complete or near complete resolution of symptoms (AOM cure), defined as an AOM-SOS score  $\leq 2$ , assessed at the Day 4 Visit, the Day 12 Visit, and the Day 28 Visit by in-clinic AOM-SOS score assessments.
- Change from baseline in AOM-SOS score over the planned 10-day treatment period by parent/caregiver diary data.
- At least a 50% reduction from baseline in the AOM-SOS score assessed at the Day 4 Visit, the Day 12 Visit, and the Day 28 Visit by in-clinic AOM-SOS score assessments.
- AOM treatment failure (clinical failure)\* at the Day 12 Visit.
- AOM relapse defined as those with clinical success# at the Day 12 Visit and who return for an interim/sick visit before Day 17 and have AOM.
- AOM recurrence defined as those with clinical success# at the Day 12 Visit and who return for an interim/sick visit from Day 17 through Day 28 and have AOM.

\*Treatment failure is defined as (1) moderate to severe bulging of the TM (Key Action Statement 1A), or (2) mild bulging of TM and recent (less than 48 hours) onset of ear pain (otalgia) (Key Action Statement 1B), or (3) mild bulging of the TM and intense erythema of the TM (Key Action Statement 1B).

#Clinical success for AOM relapse and AOM recurrence endpoints is defined as (1) no moderate to severe bulging of the TM (Key Action Statement 1A), and (2) no mild bulging of the TM

and no recent (less than 48 hours) onset of ear pain (otalgia) (Key Action Statement 1B), and (3) no mild bulging of the TM and no intense erythema of the TM (Key Action Statement 1B).

For the AOM cure endpoint, a sensitivity analysis will be done where AOM cure will be defined as AOM-SOS score = 0.

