4.2.3 Secondary Efficacy Endpoints

Secondary efficacy endpoints are:

- No MEE assessed at the Day 4 and Day 28 visits by pneumatic otoscopy
- No bulging of the TM assessed at the Day 12 and Day 28 visits by pneumatic otoscopy
- Normal tympanogram (Type A) assessed at the Day 4, Day 12, and Day 28 visits by tympanometry
- Complete or near complete resolution of symptoms (AOM cure), defined as an AOM-SOS score ≤ 2, assessed at the Day 4 Visit, the Day 12 Visit and the Day 28 Visit.
- Change from baseline in the AOM-SOS score over the 10-day planned treatment period by parent/caregiver diary data
- At least a 50% reduction from baseline in the in-clinic AOM-SOS score, assessed at the Day 4, Day 12, and Day 28 visits
- AOM treatment failure (clinical failure) at the Day 12 Visit, with treatment failure defined as moderate to severe bulging of the TM, or mild bulging of TM with recent (less than 48 hours) onset of ear pain (otalgia), or mild bulging of the TM with intense erythema of the TM.
- AOM relapse defined as those with clinical success at the Day 12 visit and who return for an interim/sick visit before Day 17 and have AOM. Clinical success is defined as no moderate to severe bulging of the TM, and no mild bulging of the TM with recent (less than 48 hours) onset of ear pain (otalgia), and no mild bulging of the TM with intense erythema of the TM.
- AOM recurrence defined as clinical success at the Day 12 visit and return for an interim/sick visit from Day 17 through Day 28 and have AOM. Clinical success is defined as no moderate to severe bulging of the TM, and no mild bulging of the TM with recent (less than 48 hours) onset of ear pain (otalgia), and no mild bulging of the TM with intense erythema of the TM.

Confidential Page 11 of 35

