6. TREATMENT ASSIGNMENT, BLINDING, AND UNBLINDING

6.1 Treatment Assignment

Following Screening, but before any treatment-related procedures, eligible subjects will be randomly assigned in a 1:1 ratio to either OP0201or placebo. The randomization schedule will be generated by the University of Pittsburgh Statistics Department. Randomization will be stratified by daycare attendance (yes, no) and age (≥ 6 to <12 months, ≥ 12 to ≤ 24 months). Daycare attendance will be defined as exposure to 3 or more children outside of the home for 10 or more hours per week. A fixed block size of 4 will be used.

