11.4 Ear Examination

Examination of each ear will be done at each study visit. Summaries, by ear and visit, will be done for: TM findings (intact, perforated,), color (gray, pink, pale yellow, white, amber, blue), translucency (translucent, semi-opaque, opaque), mobility (none, 1+, 2+, 3+, 4+), air fluid interface (yes, no), otalgia (yes, no), distinct erythema (yes, no), position of the TM (neutral, retracted, 1+ bulging, 2+ bulging, 3+ bulging), otorrhea (no, serous, purulent), and diagnosis (no effusion, OME, AOM).

Confidential Page 21 of 35

Shift tables will summarize changes from baseline in normal/abnormal status, where "abnormal" will be limited to "definitely abnormal" defined as follows:

• TM findings: perforated

• Color: pale yellow, white, amber, blue

• Translucency: semi-opaque or opaque

• Mobility: none

• Air fluid interface: yes

• Otalgia: yes

• Distinct erythema: yes

• Position of TM: retracted, 1+ bulging, 2+ bulging, 3+ bulging

• Otorrhea: serous, purulent

Diagnosis: AOM, OME

Parameters will be summarized within treatment group for (a) first or only affected ear and (b) second or non-affected ear. Since either one ear or both ears can have AOM at baseline, this approach will allow descriptive comparisons between OP0201 and placebo treatment groups on number of affected ears (ie, one or both ears) and shifts from baseline, by visit, for both affected and non-affected ears at baseline.

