12.3 Tympanogram

For a subset of the mITT population, tympanograms will be performed at each study visit to assess middle ear function. Each ear will be rated separately as Type A, Type B, or Type C.

Endpoints

Secondary endpoints based on tympanogram will be:

• Normal tympanogram (Type A) in either ear, assessed at the Day 4, 12, and 28 visits

A listing of tympanogram parameters will show peak height, gradient width, peak pressure, values derived, test results, ear canal volume value, predictive value, and rating.

Summaries and Analyses

Summary tables will include frequencies and percentages of shifts from baseline for each treatment group by visit. Crude rates of normal tympanogram by treatment group and visit will be graphically displayed using bar charts. There will be no statistical analysis of normal tympanogram.

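### SAP 12.3 lets a never-affected ear make a tympanogram count as normal, and SAP 12.4 as printed cuts AOM cure at < 2 where SAP 4.2.3 and the protocol say ≤ 2

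*SAP*

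**What the plan says.** **Tympanogram.** The protocol (1.1, Table 4 and 9.4.1) and SAP 4.2.3 list a Type A tympanogram at Days 4, 12 and 28 as a secondary endpoint. None of them says which ear, or how many ears, must be Type A. SAP 12.3 supplies a rule: "Normal tympanogram (Type A) in either ear, assessed at the Day 4, 12, and 28 visits". Each ear is rated on its own. Disease in one ear is enough for entry: "Participants with AOM in at least 1 ear will be randomly assigned to study treatment" (Protocol 1.1, Number of Participants). SAP 11.4 already arranges ear findings by baseline status, as "a) first or only affected ear and (b) second or non-affected ear". The planned outputs are shift tables from baseline and a bar chart of crude rates; SAP 12.3 adds that "There will be no statistical analysis of normal tympanogram". Appendix B gives the tympanogram subset as the population of Table 14.2.3.1, but mITT for Figure 14.2.3.

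**AOM cure.** SAP 4.2.3 has cure "defined as an AOM-SOS score ≤ 2, assessed at the Day 4 Visit", and the protocol uses the same cut-off in 1.1, Table 4 and 9.4.1. SAP 12.4, which gives the working definition, prints "defined as in-clinic AOM-SOS score < 2, assessed at the Day 4, 12, and 28 visits". On the sensitivity analysis, Protocol 9.4.1 says: "For the AOM cure endpoint, a sensitivity analysis will be done where AOM cure will be defined as AOM-SOS score = 0". SAP 12.4 repeats this.

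SAP 16 lists five changes from the protocol. Neither the ear rule nor the cure cut-off is among them.

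**The concern.** A normal-tympanogram rate should describe recovery of the diseased middle ear. Under SAP 12.3 a child with one affected ear can be displayed as normal at every visit because the other ear was healthy throughout, and a child with two affected ears needs only one to clear. The bar chart could then show a high rate that says little about recovery, in a study meant to inform later designs.

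The cure cut-off carries more analytic weight. The AOM-SOS total is calculated in the analysis data set, not on the eCRF, so the cut-off in the SAP is what gets programmed. Cure is compared between groups by logistic regression at each visit with p-values, and the endpoint was added at the regulator's request. If two sections of the SAP really do give different cut-offs, the reported cure rate depends on which one the programmer follows.

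**Working it through.** The plan gives no expected rate for either endpoint, so there is no figure to reproduce. Its power figures concern only the primary family and do not enter here.

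**A. Ear rule.** Each of two ears is Type A or not (SAP 12.3), giving 2 × 2 = 4 states. AOM at baseline is in one ear or both (Protocol 1.1; SAP 11.4). Either ear is taken in its ordinary sense of at least one ear.

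| First or only affected ear | Other ear | SAP 12.3 | Every affected ear, unilateral AOM | Every affected ear, bilateral AOM |
|---|---|---|---|---|
| A | A | normal | normal | normal |
| A | not A | normal | normal | not normal |
| not A | A | normal | not normal | not normal |
| not A | not A | not normal | not normal | not normal |
| **States counted normal** | | **3** | **2** | **1** |

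The rules disagree in 3 − 2 = 1 state for unilateral AOM (affected ear abnormal, healthy ear Type A) and in 3 − 1 = 2 states for bilateral AOM. These are logical states, not shares of children.

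For scale only, let u be the unilateral share, a the chance that an affected ear is Type A, and b the same for an unaffected ear, with ears independent:

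- SAP 12.3 rate = u[1 − (1 − a)(1 − b)] + (1 − u)[1 − (1 − a)²]
- Every-affected-ear rate = u·a + (1 − u)·a²

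None of u, a or b is in the documents. Assume a = 0.20, u from 0.3 to 0.7 and b from 0.3 to 0.9.

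- u = 0.3, b = 0.3: 0.3 × 0.44 + 0.7 × 0.36 = 0.384, against 0.3 × 0.20 + 0.7 × 0.04 = 0.088.
- u = 0.7, b = 0.9: 0.7 × 0.92 + 0.3 × 0.36 = 0.752, against 0.7 × 0.20 + 0.3 × 0.04 = 0.152.

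So the displayed rate would be 38% to 75% rather than 9% to 15%. If affected ears reach a = 0.45 in the other arm, the arm differences are:

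- u = 0.3, b = 0.3: 0.673 − 0.384 = 0.289 under SAP 12.3, against 0.277 − 0.088 = 0.189.
- u = 0.7, b = 0.9: 0.871 − 0.752 = 0.119 under SAP 12.3, against 0.376 − 0.152 = 0.224.

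The rule raises the rate in every case, but it can widen or narrow the difference between arms.

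**B. Cure cut-off.** The total is the sum of five items scored 0 to 5 (Protocol 8.2.4; SAP 12.4), so it is an integer from 0 to 25.

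| Rule | Where | Totals counted as cure |
|---|---|---|
| ≤ 2 | Protocol 1.1, Table 4, 9.4.1; SAP 4.2.3 | 0, 1, 2 |
| < 2 | SAP 12.4 as printed | 0, 1 |
| = 0 | sensitivity analysis | 0 |

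Only a total of exactly 2 is classified differently, so cure rate (≤ 2) − cure rate (< 2) = P(total = 2). The documents do not give that share; if it were 5%, 10% or 15%, the rate would move by 5, 10 or 15 percentage points. Under < 2, the main analysis would differ from the sensitivity analysis only by children scoring 1.

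**C. Is the < real?** Outside SAP 12.4, the machine-read SAP text has three ≤ signs, and all three are recoverable: in 4.2.3, in 6.1 ("≥ 6 to <12 months, ≥ 12 to ≤ 24 months"), and in 8.4, where the sign appears as a typesetting code. That makes a true typing error possible. Against it, SAP 8.6 keeps the minus sign in the study-time formula and loses it in four others (two for study day, two for duration), so this text drops symbols erratically. The text cannot settle the matter; the source page can.

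**The case against.** The strongest reply on cure is that the discrepancy rests on one character in text known to lose symbols, while four other statements agree on ≤ 2 and SAP 16 declares no change. That silence suggests ≤ 2 was meant throughout. This stands: no more than a possible error can be claimed, and the first step is to look at the page.

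On the tympanogram, the sponsor can say that the protocol gives no ear rule for the SAP to contradict, that nothing is tested, that shift tables show where each result started, and that requiring every affected ear is one choice among several. Most of this also stands. A reader might infer that SAP 12.3 departs from the protocol; it does not, because it fills a gap, and fills it weakly. What survives is that the rule, followed as written, credits a child with recovery through an ear that was never diseased.

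On the figure's population, SAP 12.3 says that tympanograms cover a subset of mITT, SAP 8.2 defines n as non-missing observations, and SAP 8.5 rules out imputation in summaries. The mITT entry is a label to tidy, not a wrong denominator.

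A reader might also infer that the protocol and SAP define clinical success differently and so give different risk sets for relapse and recurrence. Read literally, the protocol wording is stricter, but it can equally be read as negating each paired criterion, which matches the SAP. Status is taken from the eCRF and not derived (SAP 12.6), and the eCRF is not among the documents. No mismatch and no changed value can be shown, so nothing is claimed there.

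**Conclusion.** Both points hold, within limits. The ear rule is a weak definition whatever the quality of the PDF. It accepts three of four ear states where a rule tied to affected ears accepts two or one, and its reach is the descriptive crude-rate bar chart. The cure cut-off is inconsistent as printed. If the sign is real, every child with a total of exactly 2 is excluded from cure at Days 4, 12 and 28, and tested results change by an amount the documents do not allow one to state.

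The percentages for the ear rule rest on assumed rates and independent ears, and only illustrate scale. A reader might infer that the either-ear rule biases the comparison against the drug; the same arithmetic shows that the difference can move either way. Both endpoints are secondary and have no multiplicity control, so the primary family, its alpha and the power are untouched.

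**What to change.** 1. In SAP 12.3, for the crude-rate display, define normal tympanogram as Type A in every ear affected at baseline. The data are already there: SAP 11.4 summarises diagnosis by ear and visit, and SAP 8.4 uses baseline laterality. Because the second category in 11.4 pools second affected ears with unaffected ones, program the restriction from each ear's baseline diagnosis rather than from that category.
2. In Appendix B, label Figure 14.2.3 with the tympanogram subset, as Table 14.2.3.1 is.
3. Check the source page of SAP 12.4. If it shows ≤ 2, the point closes. If it shows < 2, correct it to ≤ 2 to agree with SAP 4.2.3 and the protocol.

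The cost is one page check, a few words in the SAP, and an ear restriction and population label on one descriptive figure. There is no new data collection and no burden on participants.
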